### 10.3.4 Early Termination of Subjects from the Study

Subject participation in this trial may be discontinued for any of the following reasons:

1. Occurrence of any medical condition or circumstance that exposes the subject to substantial risk and/or does not allow the subject to adhere to the requirements of the protocol.
2. Any SAE, clinically significant AE, severe laboratory abnormality, intercurrent illness, or other medical condition that indicates to the PI or designee that continued participation is not in the best interest of the subject.
3. Subject's decision to withdraw.
4. Requirement of prohibited concomitant medication.
5. Subject failure to comply with protocol requirements or study related procedures.
6. Termination of the study by the Sponsor, FDA, Celerion, or other regulatory authorities.
7. Pregnancy.

The clinical report will include reason(s) for subject withdrawals as well as details relevant to the subject withdrawal. If a subject is withdrawn from the trial prior to study completion, the subject will undergo all procedures scheduled for subjects who terminate early (see [Section 6](#)) as the situation allows (see [Section 10.2.4](#)). Any subject withdrawn due to an AE (whether serious or non-serious) or clinically significant abnormal laboratory test values will be evaluated by the PI or designee or a monitoring physician and will be treated and/or followed up until the symptoms or values return to normal or acceptable levels, as judged by the PI or designee.

Subjects withdrawn may be replaced at the Sponsor's discretion.

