#### **10.4.1.4 Dose Escalation and Stopping Rules**

Dose escalation to the next dose level (i.e., next cohort) will not take place until after the PI has reviewed the safety data. If any findings in the safety data are of concern, then the SRC comprised of but not limited to, the Sponsor, medical monitor, and the PI will convene to determine if adequate safety and tolerability from the previous cohort has been demonstrated to permit proceeding to the next cohort. The SRC review of all pertinent blinded safety/tolerability data must comprise of physical examinations, ECGs, vital signs, clinical laboratory tests [including coagulation], thrombin time, injection site reaction, and AEs available for all subjects who have completed up to Day 14 procedures.

Data from all subjects in the cohort will be used and reviewed for a dose escalation decision and a minimum of 4 subjects must complete the study (up to Day 14) before proceeding to the next higher dosing cohort.

Together they will make one of the following determinations:

1. To continue with the study as planned.
2. To continue with the study and add additional safety evaluations.
3. To continue with the study and repeat a cohort.

4. To continue with the study by adjusting to an intermediate dose between the current dose and the previous lower dose (i.e., add an additional cohort) or to repeat a cohort, if:
  - a. At least 1 subject has a SAE or visit to the emergency room deemed to be possibly study drug related (see [Section 11.1.8.4](#)).
  - b. At least 25% of subjects in a cohort experience a grade  $\geq 2$  AE deemed to be possibly related to the study drug.
5. To stop the study. The study will be terminated if the following number of subjects meet any of the following criteria and the subjects were determined to have received active drug after unblinding:
  - I.  $\geq 1$  subject that receive drug in a cohort experience:
    - a. Life-threatening hypersensitivity reactions (e.g., anaphylaxis, respiratory symptoms, hypotension etc.).
    - b. Any grade thromboembolic event possibly related to the study drug.
    - c. Any grade bleeding possibly related to the study drug.
    - d. Presence of antibodies against human thrombin or prothrombin.
    - e. Presence of ADA.
  - II.  $\geq 2$  subjects that receive drug in a cohort:
    - a. Has a drug possibly or probably related SAE (see [Section 11.1.8.4](#)).
    - b. Experiences a drug related grade  $\geq 3$  toxicity (see [Section 11.1.8.3](#)).

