## 4. ANALYSIS POPULATIONS

### 4.1 Analysis Populations

**Safety population:** All subjects who received the study drug (active or placebo) will be included in the safety summary.

**PD population:** All subjects receiving the study drug (active or placebo) and having any measurable PD data will be included in the PD data set. The Sponsor will assess the real time aPTT on-site. The protein C samples will be processed by Celerion associates and then shipped to Aronora for later analysis.

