## **8. SAFETY**

No inferential statistics will be performed on the safety endpoints.

All Case Report Form (CRF) data will be listed by subject and chronologically by assessment time points. This will include rechecks, unscheduled assessments, and early termination results.

Applicable continuous variables will be summarized using the number of observations (n), mean, SD, minimum, median, and maximum. Frequency counts will be reported for categorical data, when appropriate. The placebo subjects from all cohorts will be pooled into a single group for summarization.

The level of precision will be presented as follows: minimum/maximum in the same precision as in the database, mean/median in one more precision level than minimum/maximum, SD in one more precision level than mean/median, and n will be presented as an integer.

For laboratory, ECGs, and vital signs, where individual data points are missing because of dropouts or other reasons, the data will be summarized based on reduced denominators.

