Appendix 16.2.2 Protocol Deviations

##### **16.2.3 Subjects Excluded from Pharmacodynamic Analysis**

Appendix 16.2.3 Subjects Excluded from  
Pharmacodynamic/Immunogenicity Analysis

Note: Appendices 16.2.2 and 16.2.3 are generated in MS Word for inclusion in the study report.

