**Programmer Notes:**

- This is just a mock table shell. Please use the race categories listed in the CRF.
- Height (cm) and BMI (kg/m^2) will be also summarized in this table.

In-text Table 11-2 will be in the following format.

Table 11-2 Summary of APC-PCI Following Administration of a Single IV Dose of 0.5, 1.0, 2.0, and 4.0 mcg/kg E-WE Thrombin

Hour	0.5 mcg/kg (N=X)	1.0 mcg/kg (N=X)	2.0 mcg/kg (N=X)	4.0 mcg/kg (N=X)	Placebo (N=X)
XX	X ± X	X ± X	X ± X	X ± X	X ± X
XX	X ± X	X ± X	X ± X	X ± X	X ± X
XX	X ± X	X ± X	X ± X	X ± X	X ± X
XX	X ± X	X ± X	X ± X	X ± X	X ± X

N is the total number of subjects dosed at each dose level.  
Source: Table XXX

Treatments:

- 0.5 mcg/kg E-WE thrombin (IV bolus)
- 1.0 mcg/kg E-WE thrombin (IV bolus)
- 2.0 mcg/kg E-WE thrombin (IV bolus)
- 4.0 mcg/kg E-WE thrombin (IV bolus)
- Pooled Placebo (IV bolus)

Programmer's note:

- Arithmetic mean ± SD will be presented.
- Table 11-2 the source table will be 14.2.1.1 through 14.2.1.5.

In-text Tables 11-3 and 11-4 will be in the following format.

Table 11-3 Summary of Anti- E-WE Thrombin Plasma ADA Following Administration of a Single IV Dose of 0.5, 1.0, 2.0, and 4.0 mcg/kg E-WE Thrombin

	0.5 mcg/kg (n=x)	1.0 mcg/kg (n=x)	2.0 mcg/kg (n=x)	4.0 mcg/kg (n=x)	Placebo (n=x)
Predose (Day -1)					
ADA Test Result Number Negative/Positive	X/X	X/X	X/X	X/X	X/X
Confirmatory E-WE Thrombin Positive	X	X	X	X	X
Neutralizing Positive	X	X	X	X	X
Day 14					
ADA Test Result Number Negative/Positive	X/X	X/X	X/X	X/X	X/X
Confirmatory E-WE Thrombin Positive	X	X	X	X	X
Neutralizing Positive	X	X	X	X	X
Day 28					
ADA Test Result Number Negative/Positive	X/X	X/X	X/X	X/X	X/X
Confirmatory E-WE Thrombin Positive	X	X	X	X	X
Neutralizing Positive	X	X	X	X	X

Presentation of Data:

- The following outcomes will be presented as number of subjects (% of the population): confirmatory positive will be a percentage of the total subject in the dose level
- Number of subjects will be presented as an integer (no decimals)
- 4 dose levels will be presented instead on the same table
- Internal Table template: Table ITPar1

Programmer's note:

- Table 11-3 the source table will be 14.2.2.1.
- Table 11-4 the source table will be 14.2.2.2.
- ADA collection times: Predose, Day 14 and Day 28 postdose.

Program: /CAXXXXX/sas\_prg/pksas/intext-pk-tables.sas DDMMYYYY HH:MM  
Program: /CAXXXXX/sas\_prg/pksas/adam\_intext\_pkparam.sas DDMMYYYY HH:MM

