**Tables 14.2.2.1 and 14.2.2.2 will be in the following format.**

Table 14.2.2.1 Plasma Anti-E-WE Thrombin Antibody Detection Following Administration of a Single IV Dose of 0.5, 1.0, 2.0, or 4.0 mcg/kg E-WE Thrombin Summary by Collection Time and Treatment - Number of Subjects (% Total Subjects)

Test	Result	0.5 mcg/kg				1.0 mcg/kg			
		Day X	Day X	Day X	Overall*	Day X	Day X	Day X	Overall*
		N=X	N=X	N=X	N = X	N=X	N=X	N=X	N = X
Initial	Negative	X (X%)	X (X%)	X (X%)	X (X%)	X (X%)	X (X%)	X (X%)	X (X%)
	Positive	X (X%)	X (X%)	X (X%)	X (X%)	X (X%)	X (X%)	X (X%)	X (X%)
Confirmatory	Negative	X (X%)	X (X%)	X (X%)	X (X%)	X (X%)	X (X%)	X (X%)	X (X%)
	Positive	X (X%)	X (X%)	X (X%)	X (X%)	X (X%)	X (X%)	X (X%)	X (X%)
Neutralizing	Negative	X (X%)	X (X%)	X (X%)	X (X%)	X (X%)	X (X%)	X (X%)	X (X%)
	Positive	X (X%)	X (X%)	X (X%)	X (X%)	X (X%)	X (X%)	X (X%)	X (X%)

N is the total number of subjects dosed at each dose level.

Programmer Note:

- Immunogenicity sampling times: Day -1, Day 14, and Day 28
- Treatments:
  - 0.5 mcg/kg E-WE thrombin (IV bolus)
  - 1.0 mcg/kg E-WE thrombin (IV bolus)
  - 2.0 mcg/kg E-WE thrombin (IV bolus)
  - 4.0 mcg/kg E-WE thrombin (IV bolus)
  - Pooled Placebo: Placebo Solution (IV bolus)

Note: \* if the response of a subject is positive at least once postdose, it will be counted as "positive"; otherwise will be considered as "negative".

Only screening positives will be reassayed for confirmatory analysis.

Program: /AAXXXXX/ECR/sas\_prg/pksas PROGRAMNAME.sas DDMMYYYY HH:MM

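### The *Overall* column of the SAP's ADA detection tables counts a dosed subject with no evaluable post-dose sample as ADA-negative

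*SAP*

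**What the plan says.** SAP 7 provides for ADA samples on Day -1, Day 14 and Day 28, so each subject has two post-dose samples, both taken after discharge. It gives no rule for a missing sample.

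The shell for Tables 14.2.2.1 (plasma, anti-E-WE) and 14.2.2.2 (serum, anti-wild-type) in SAP 11.2 has a column for each visit and an *Overall* column. Each test level has two result rows, Negative and Positive. The footnote to *Overall* says that "if the response of a subject is positive at least once postdose, it will be counted as" positive, and assigns all remaining subjects to negative. The denominator is defined in the same place: "N is the total number of subjects dosed at each dose level".

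In-text Tables 11-3 and 11-4 draw on these two tables. They have rows by visit and no *Overall* row. Their note says "confirmatory positive will be a percentage of the total subject in the dose level".

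**The concern.** The footnote has two outcomes for what are really three kinds of subject: positive after dosing, tested and not positive, and never tested after dosing. The third kind falls into the negative row by default, and the denominator of all dosed subjects keeps it there.

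Immunogenicity is a named safety assessment in both documents, and these tables are its summary by dose level. A subject with no post-dose result carries no information about antibody formation. In groups of 4, a single such subject visibly changes the printed rate, and whenever there is a positive the change is downward.

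**Working it through.** **Inputs.** Group sizes come from Protocol 10.3.1 and SAP 3: 4 active subjects in each of four cohorts, with 2, 1, 1 and 1 placebo subjects. Active: 4 × 4 = 16. Placebo, pooled: 2 + 1 + 1 + 1 = 5. Total: 16 + 5 = 21, which is the planned enrolment. The documents state no ADA rate and no dropout rate, so the numbers untested (m) and positive (x) below are assumptions.

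**Does another SAP rule remove the untested subject?**

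- *Reduced denominators (SAP 8).* The rule opens "For laboratory, ECGs, and vital signs, where individual data points are missing because of dropouts or other reasons". SAP 8.4 takes laboratory tests to be serum chemistry, hematology, coagulation and urinalysis. SAP 2.2 lists immunogenicity separately from clinical laboratory tests. ADA is not covered.
- *Populations (SAP 4.1).* There is a Safety population and a PD population. The latter is for subjects "having any measurable PD data will be included in the PD data set", which turns on PD data and not ADA data. No immunogenicity population is defined, and the ADA detection tables carry no population label.
- *Appendix 16.2.3.* Its title covers subjects excluded from "Pharmacodynamic/Immunogenicity Analysis", but the SAP gives no criterion for exclusion.
- *Missing-value convention.* The APC-PCI shell (Tables 14.2.1.1 to 14.2.1.5) has an n row and a symbol for a missing value. The ADA detection shell has neither.

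None of the four changes the classification or N.

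**Size.** Under the SAP rule the positive rate is x/N. Among evaluable subjects it is x/(N − m).

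| Group | N dosed | m untested | x positive | SAP rule, x/N | Evaluable, x/(N − m) | Difference (points) |
|---|---|---|---|---|---|---|
| Active dose level | 4 | 0 | 1 | 1/4 = 25.0% | 1/4 = 25.0% | 0 |
| Active dose level | 4 | 1 | 1 | 1/4 = 25.0% | 1/3 = 33.3% | −8.3 |
| Active dose level | 4 | 2 | 1 | 1/4 = 25.0% | 1/2 = 50.0% | −25.0 |
| Pooled placebo | 5 | 1 | 1 | 1/5 = 20.0% | 1/4 = 25.0% | −5.0 |

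Because N ≥ N − m, x/N can never exceed x/(N − m). The two agree when m = 0 or x = 0.

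With x = 0 the rate is 0% either way, but the evidence behind it is overstated. For N = 4 and m = 1, 3 of 3 negative prints as 4 of 4. The exact 95% upper limit for zero positives is 1 − 0.025^(1/n): 60.2% for n = 4, 70.8% for n = 3 and 84.2% for n = 2. The SAP plans no such interval; it is given here only to show what the extra negative implies.

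**The case against.** The strongest defence is that the footnote speaks of a subject's response and so presupposes that one exists. On that view its default branch only lets the tiered assay resolve to negative when no confirmatory test is run. SAP 11 says the shells show general layout and may change. Appendix 16.2.3 shows that exclusions from immunogenicity analysis were contemplated. Subjects who terminate early are asked to return on Days 14 and 28 for immunogenicity sampling (Protocol 10.1.1), so few may lack both samples. If one does, the visit columns fall short of N and a careful reader could see it. No inference is planned, and the exact 95% intervals for 1/3 (0.8% to 90.6%) and 1/4 (0.6% to 80.6%) largely overlap.

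Much of this limits the effect, and that part stands. It does not remove the rule. A written classification with a stated N is an instruction to the programmer, not layout, and N as all dosed subjects with no missing category does not fit the narrower reading. Asking subjects to return makes a missing sample less likely but does not say how to report one.

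Three stronger readings are tempting, and the documents do not support them:

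- *The escalation rule shows how many subjects would be misreported.* Protocol 10.4.1.4 requires that "a minimum of 4 subjects must complete the study (up to Day 14) before proceeding to the next higher dosing cohort", in cohorts of 6 or 5. That concerns Day 14 only. A subject who misses Day 14 but has an evaluable Day 28 sample is correctly classified in *Overall*. Nor does withdrawal or replacement imply that a subject is untested.
- *SAP 7 restricts the check-in assay to subjects positive at both visits.* SAP 7 refers to detection on Days 14 and 28, where Protocol 10.1 has and/or. Footnote l of the protocol's flow chart uses the same pair of days to name the visits sampled, and makes any ADA finding the trigger. The SAP wording is best read the same way.
- *Tables 11-3 and 11-4 contain the same default.* They have no *Overall* row and print negative and positive counts by visit, so an untested subject is not turned into a negative there. Only their percentage denominator needs attention.

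**Conclusion.** The point holds as a minor reporting defect. As written, *Overall* in Tables 14.2.2.1 and 14.2.2.2 reports a dosed subject with no evaluable post-dose ADA result as negative, and no other SAP rule corrects it. One such subject among 4 costs 8.3 percentage points when there is one positive, and adds one unsupported negative when there is none.

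This rests on the literal text of the shell and on an assumed number of untested subjects. It arises only if both the Day 14 and Day 28 samples are missing or not evaluable; with at least one evaluable post-dose result for every dosed subject, *Overall* is correct. A reader might infer that the rule could mask an ADA signal during the study. It could not: the stopping criterion in Protocol 10.4.1.4 acts on ADA in individual subjects and does not use this column.

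**What to change.** 1. In *Overall* of Tables 14.2.2.1 and 14.2.2.2, classify as negative only subjects with at least one evaluable post-dose result and none positive. Use subjects with at least one evaluable post-dose result as the denominator, and add a not-evaluable row so that the counts still add up to all dosed subjects. State that a negative screening result is evaluable, so that subjects not sent on to the confirmatory assay remain negative.
2. In the visit columns of these tables and the visit rows of Tables 11-3 and 11-4, use the number of subjects with an evaluable result at that visit. An any-post-dose denominator would be wrong there, because it would keep a subject sampled only on Day 28 in the Day 14 denominator.
3. Show Day -1 as counts only, with a footnote that check-in samples are assayed only after a post-dose positive.
4. Optional wording: align SAP 7 with the and/or of Protocol 10.1.

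The cost is a few lines of SAP and shell text and minor programming. It needs no new samples or assays and changes neither study conduct nor the stopping rule.

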**Tables 14.2.2.3 through 14.2.2.4 will be in the following format:**

Table 14.2.2.3 Summary of Titers for Plasma Anti-E-WE Thrombin Antibody

Subject	0.5 mcg/mL	1.0 mcg/mL
X	XX	XX
n	X	X
Mean	XX.X	XX.X
SD	X.XX	X.XX
Minimum	XX	XX
Median	XX.X	XX.X
Maximum	XX	XX

Note: 0.5 mcg/kg: 0.5 mcg/kg E-WE thrombin (IV bolus)  
 1.0 mcg/kg: 1.0 mcg/kg E-WE thrombin (IV bolus)  
 2.0 mcg/kg: 2.0 mcg/kg E-WE thrombin (IV bolus)  
 4.0 mcg/kg: 4.0 mcg/kg E-WE thrombin (IV bolus)  
 Pooled Placebo: Placebo Solution (IV bolus)

Programmer note: if the screening result is negative, confirmatory and titer assays will not be performed. If confirmatory result is negative, but the screening was positive, the titer assay will not be performed.

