**Note: Figures of 14.2.4.1 and 14.2.4.3 will be in the following format.**

Figure 14.2.4.1 Summary of Titers for Plasma Anti-E-WE Thrombin Antibody by Treatment - Line Plot (Mean  $\pm$  SD) for Confirmatory Test Results

[figure not shown]

Programmer Note: If data for neutralizing test are available, please present similar figure. Plots to be generated in SAS.

Program: /CAXXXXX/sas\_prg/stsas/lis\_PROGRAMNAME.sas DDMMYYYY HH:MM

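### SAP Tables 14.2.2.1 and 14.2.2.2: the Overall column would report a confirmed ADA-positive subject as neutralizing-negative if no neutralizing assay was run on that subject

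*SAP*

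**What the plan says.** The shell in SAP 11.2 shared by Tables 14.2.2.1 (plasma anti-E-WE thrombin) and 14.2.2.2 (serum anti-wild-type thrombin) has Negative and Positive rows for each of three tests: Initial, Confirmatory and Neutralizing. Each dose level has day columns and an Overall column. An asterisk on the Overall header leads to the classification rule: "if the response of a subject is positive at least once postdose", the subject counts as positive, and in every other case as negative. The denominator is stated as "N is the total number of subjects dosed at each dose level". There is no row for not tested or not done.

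The same notes restrict the second tier: "Only screening positives will be reassayed for confirmatory analysis". The note under Table 14.2.2.3 agrees: "if the screening result is negative, confirmatory and titer assays will not be performed".

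For the third tier, protocol 11.1.7 describes only the E-WE thrombin and wild-type thrombin ADA assays, and SAP 7 mentions only the confirmatory assay and titers. The neutralizing test appears in the table shells and, conditionally, in the titer figure shells: "If data for neutralizing test are available, please present similar figure". No text says which samples would be tested.

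**The concern.** The Overall rule has two states, positive and negative, but the testing is sequential and needs a third: not assayed at this tier. Under the rule, absence of a test is reported as a negative test.

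This matters most in the Neutralizing row. A confirmed ADA-positive subject is the one for whom neutralizing status is informative. Protocol 10.4.1.2 shows that neutralizing antibody to thrombin/prothrombin is a matter the trial watches for, using thrombin time and aPTT. A row showing every subject neutralizing-negative would look like evidence of absence when no such assay had been done. In the Confirmatory row the same rule puts subjects never reassayed together with subjects who screened positive and failed confirmation.

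**Working it through.** **Inputs.** Protocol 10.3.1 plans 4 active subjects per dose level and 2 + 1 + 1 + 1 = 5 placebo subjects. The total is 4 × 4 + 5 = 21, which matches the stated 21. The plan gives no expected ADA rate, so the result counts below are assumed and varied.

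**Notation, per group.** N = dosed, s = screened positive, c = confirmed positive, t = confirmed positives assayed for neutralization, q = neutralizing-positive.

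**What the Overall rule prints.**
- Confirmatory Negative = N − c. This is the sum of (N − s) never reassayed and (s − c) reassayed and not confirmed.
- Neutralizing Negative = N − q. Only t − q of these have a negative result, and c − t are confirmed positives with no neutralizing result.

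**Neutralizing row with no assay run (t = 0, q = 0).**

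| Group | s | c | Printed negative | Assays run | Confirmed positives printed negative |
|---|---|---|---|---|---|
| Dose level, N = 4 | 0 | 0 | 4 (100%) | 0 | 0 |
| Dose level, N = 4 | 1 | 1 | 4 (100%) | 0 | 1 |
| Dose level, N = 4 | 2 | 1 | 4 (100%) | 0 | 1 |
| Dose level, N = 4 | 4 | 4 | 4 (100%) | 0 | 4 |
| Pooled placebo, N = 5 | 1 | 1 | 5 (100%) | 0 | 1 |

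The printed figure is 100% negative whatever c is. A reader who took 0/4 positive at face value could attach an exact one-sided 95% upper limit of 1 − 0.05^(1/4) = 52.7%, although the data give no estimate at all.

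**If every confirmed positive is assayed (t = c).** Then c − t = 0 and no confirmed positive is misreported. With N = 4, c = t = 1 and q = 0, the row prints 4 negative: one tested negative and three who had no confirmed ADA and were not assayed.

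**Confirmatory row, N = 4.** With s = 1 and c = 1, Overall prints 3 negative (75%) and 1 positive (25%), although none of the 3 was reassayed. With s = 0, c = 0 and with s = 1, c = 0, the row prints 4 negative both times. The Initial Positive row separates these two cases (0 against 1), and s − c gives the number not confirmed.

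**The case against.** The best defence is that the effect is narrow, and much of that stands.

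- **Scope.** The asterisk is on the Overall header only. The day columns carry no such rule; they are silent on untested subjects rather than wrong. A reader might infer that in-text Tables 11-3 and 11-4 share the error. They do not: they have no Overall column and no negative row at the confirmatory or neutralizing tier, only a "Neutralizing Positive" row for the latter. Their note that "confirmatory positive will be a percentage of the total subject in the dose level" describes an ordinary incidence.
- **Whether an assay is planned.** It is tempting to say that none is. The documents support less: none is described in protocol 11.1.7 or SAP 7, but the shells provide for one conditionally. As the working shows, a confirmed positive is misreported only if that subject is not assayed.
- **Screening performance.** A reader might think that the number of unconfirmed screening positives is lost. It is not. All screening positives are reassayed, so Initial Positive minus Confirmatory Positive in the same column gives it.
- **Confirmatory row.** A screening-negative subject is ADA-negative under the tiered scheme, and the notes tell the reader that such subjects are not reassayed. Final ADA status does not change, so this part is labelling. If all 21 subjects screened negative, the printed negatives would likewise hide no known ADA carrier.
- **Decisions.** The stopping rules in protocol 10.4.1.4 act on ADA and on antibodies to human thrombin or prothrombin, and escalation uses aPTT, PT, thrombin time, the mixing study and ADA data. None uses the neutralizing row. A confirmed positive also remains visible as Confirmatory Positive and in the titer and duration tables.
- **Shells may change.** SAP 11 says so. But this footnote is a classification rule rather than layout, and SAP 7 supplies no other rule. The conditional wording on neutralizing data is attached to the figures, not to these tables.

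None of this removes the Neutralizing entry in the Overall column: followed as written, the rule gives a wrong result for an untested confirmed positive.

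**Conclusion.** The point holds for the Overall column of Tables 14.2.2.1 and 14.2.2.2. If a confirmed-positive subject is not assayed for neutralization, the stated rule prints that subject as neutralizing-negative. With one confirmed positive among 4 and no assays, it prints 4/4 negative from 0 tests. This rests on a literal reading of the footnote, the planned group sizes and an assumed confirmed positive who is not assayed; it disappears for confirmed positives if all of them are tested. The Confirmatory part is a labelling fault only. Severity is minor: a reporting error with no effect on confirmed ADA status, stopping or escalation.

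**What to change.** In the Overall column of Tables 14.2.2.1 and 14.2.2.2:

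1. Count a subject as negative at a tier only if there is a postdose result at that tier.
2. State in SAP 7 whether a neutralizing assay will be run and on which samples. If it is, report positive, negative and not tested among confirmed positives. If it is not, delete the Neutralizing rows or print not done.
3. In the Confirmatory block, show screening negatives on their own line as not reassayed.
4. Keep confirmed ADA positive as a proportion of the dose level.

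The cost is a revised footnote, a sentence in SAP 7, a few shell rows and minor programming. No new samples or assays are needed.
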